10.4 Performance Status

Patients will be graded according to the Zubrod Performance Status Scale.

POINT	DESCRIPTION
0	Fully active, able to carry on all pre-disease performance without restriction.
1	Restricted in physically strenuous activity but ambulatory and able to carry out work of a light or sedentary nature, e.g., light housework, office work.
2	Ambulatory and capable of self-care but unable to carry out any work activities; up and about more than 50% of waking hours.
3	Capable of limited self-care, confined to bed or chair more than 50% of waking hours.
4	Completely disabled; cannot carry on any self-care; totally confined to bed or chair.

10.5 Progression-Free Survival (PFS)

From date of registration to date of first documentation of progression or symptomatic deterioration (as defined above), or death due to any cause. Patients last known to be alive without report of progression are censored at date of last contact.

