7.7 Follow-Up Period

All patients will be followed until death or 3 years after registration, whichever occurs first.

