- A To be performed on or prior to Day 1 and on Day 21-35 (Day 28 +/- 7 days). The first biopsy should be performed within 28 days prior to Day 1. If it is not feasible to obtain this biopsy, tissue that was collected at any time since demonstrated progression on PD-1 or PD-L1 therapy may be substituted provided that 30 unstained slides are available.
- B Only for patients with symptoms of congestive heart failure (CHF), cardiomyopathy, myocarditis, myocardial infarction, or exposure to cardiotoxic medications. Required pre-registration (see [Section 5.3n](#)). After that, perform as clinically indicated.
- C Free T3 and Free T4 are only required if TSH results are abnormal.
- D Only for patients with a known history of congestive heart failure (CHF), cardiomyopathy, myocarditis, myocardial infarction, exposure to cardiotoxic medications, or with a clinical history suggestive of any of these conditions. Required pre-registration (see [Section 5.3m](#)). After that, perform as clinically indicated.
- E Collected prior to previous anti-PD-1 or anti-PD-L1 treatment
- F To be drawn on or prior to Day 1 (after registration and within 28 days) and on Day 21-35 (Day 28 +/- 7 days). If feasible, Day 1 blood should be drawn on the same day as the baseline tissue biopsy. Day 28 Blood must be drawn on same day as the Day 28 tissue biopsy.
- G Required time frame is detailed in [Section 5.0](#).
- H Only for females of reproductive potential (see [Section 5.3p](#))
- J Only required for patients with a known history of HIV (see [Section 5.3g](#))
- K Weeks measured from start of treatment, provided that the patient does not have any treatment delays
- L If pre-registration exam/lab was performed within 14 days prior to Cycle 1 Day 1, this exam/lab does not need to be repeated on Cycle 1 Day 1.
- M Performed at completion of Week 12
- N Every 12 weeks until progression
- P Every 3 weeks until resolution of adverse events
- Q At least every 6 months (+/- 2 weeks) until 2 years after registration, then annually (+/- 4 weeks) until 3 years after registration.
- R Though weight should be checked at each visit, weight-based dosing should be calculated using baseline weight unless weight has changed from last dose by more than 10%.

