9.3 Arm 2 Cycles 5+

	Cycle (1 cycle = 28 days) ^R												Follow-up prior to progression	Follow-up after progression
	5				6				7+					
	Week ^K													
	13	14	15	16	17	18	19	20	21	22	23	24		
PHYSICAL														
History and physical exam	X				X				X				X ^N	X ^Q
Weight and performance status	X				X				X				X ^N	X ^Q
Toxicity notation	X				X				X				X ^P	X ^P
Disease assessments												X ^M	X ^M	
LABORATORY														
ANC, platelets, and hemoglobin	X				X				X				X ^P	X ^P
AST, ALT, and total bilirubin	X				X				X				X ^P	X ^P
Serum creatinine	X				X				X				X ^P	X ^P
Creatinine phosphokinase (CPK), Troponin, and Cardiology consultation ^B														
TSH, Free T4, Free T3 ^C	X				X				X					
X-RAYS AND SCANS														
MRI or CT for disease assessment ^S												X ^M	X ^M	
Electrocardiogram (ECG) and Echocardiogram (Echo) ^D														
TREATMENT														
Nivolumab 480 mg	X				X				X					

Click here for [footnotes](#).

Note: Forms are found on the protocol abstract page of the SWOG website (www.swog.org). The schedule for submission of these forms is listed in [Section 14.0](#).

Note: Unless indicated otherwise in the protocol, scheduled procedures and assessments (treatment administration, toxicity assessment, disease assessment, specimen collection and follow-up activities) must follow the established SWOG guidelines as outlined in <http://swog.org/Visitors/QA/Documents/Best%20Practices%20update.pdf>.

Footnotes

- B Only for patients with symptoms of congestive heart failure (CHF), cardiomyopathy, myocarditis, myocardial infarction, or exposure to cardiotoxic medications. Required pre-registration (see [Section 5.3n](#)). After that, perform as clinically indicated.
- C Free T3 and Free T4 are only required if TSH results are abnormal.
- D Only for patients with a known history of congestive heart failure (CHF), cardiomyopathy, myocarditis, myocardial infarction, exposure to cardiotoxic medications, or with a clinical history suggestive of any of these conditions. Required pre-registration (see [Section 5.3m](#)). After that, perform as clinically indicated.
- K Weeks measured from start of treatment, provided that the patient does not have any treatment delays
- M Performed every 12 weeks (i.e., at *completion* of Week 24, 36, etc.) for 3 years from time of registration or until progression.
- N Every 12 weeks until progression
- P Every 4 weeks until resolution of adverse events

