10.6 Time to death

Measured from the date of registration until death from any cause, with patients last known to be alive censored at the date of last contact

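### PFS is censored at last contact, so patients who stop disease assessment but stay in contact count as progression-free for time in which nobody looked for progression

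*Combined protocol and SAP*

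**What the plan says.** Section 10.5 defines PFS as running "From date of registration to date of first documentation of progression or symptomatic deterioration (as defined above), or death due to any cause". Everyone else falls under one sentence: "Patients last known to be alive without report of progression are censored at date of last contact". Section 10.6 uses the same date for time to death, "with patients last known to be alive censored at the date of last contact".

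Disease assessments are due at the end of Week 12 and then at 12-week intervals in both arms: "Every 12 weeks until progression" in the study calendar and, for Arm 2 from Cycle 5, "for 3 years from time of registration or until progression". Contact can go on much longer than scanning, because Section 7.7 says "All patients will be followed until death or 3 years after registration, whichever occurs first".

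Section 11.2 names a log-rank test and Kaplan-Meier medians for PFS. Neither Section 10 nor Section 11 says how to treat missed or stopped assessments, and no sensitivity analysis on censoring is planned.

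**The concern.** Last contact suits survival, where any contact settles the patient's status. It does not suit PFS. Section 10.2 itself says that trials with a progression endpoint need whole-body scanning at set intervals to show that progression is absent, and it has a category for status unknown because assessment was inadequate. Section 10.5 nevertheless carries a patient of unknown status forward as progression-free.

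The rule acts in two ways. A patient who stops scanning and is still alive at the analysis stays in the PFS risk set to last contact. A patient who stops scanning, progresses unseen and later dies is an event, but at the date of death. With an assumed median of 9 months from progression to death, that delay is large beside the 3-month difference in medians (3 against 6 months) that the trial is designed to detect.

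This is the primary endpoint of a small trial (63 against 21 eligible patients, one-sided 10% test), so a handful of such patients can move the result.

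**Working it through.** **Inputs from the plan (Sections 11.1 and 11.2).** 63 combination and 21 ipilimumab patients; exponential PFS with medians of 6 and 3 months (hazard ratio 0.5); 24 months of accrual plus 12 of follow-up; one-sided 10% log-rank test. Assessments every 12 weeks (Section 9).

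**Assumptions not in the plan.** A share of patients progression-free at Week 12 stop scanning but stay in contact. Median time from progression to death is 9 months. Stoppers have no recorded PFS event before death.

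**The plan's own figures.** Section 11.2 states 89% power and 9.0% type I error, with a futility look.
- Schoenfeld approximation with 78 events and no look: √(78 × 0.25 × 0.75) × ln 2 − 1.282 = 3.824 × 0.693 − 1.282 = 1.37, so power is 91.5%.
- Simulation of the stated design with the look at 41 events: 91.9% power and 11.6% type I error.

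The stated pair is therefore not reproduced on a literal reading. That is a separate matter and does not affect this point. The runs below omit the futility look; with nobody stopping they give about 11% type I error and 91-92% power.

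**How many patients are involved.** Week 12 is 84/30.44 = 2.76 months. With a 3-month median, the progression-free share is exp(−0.693 × 2.76/3) = 0.53. At 20% and 10% stopping under the null: 63 × 0.53 × 0.20 + 21 × 0.53 × 0.10 = 6.7 + 1.1, or about 8 of 84 patients.

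**Results.** 4,000 simulated trials per row; the Monte Carlo error at 16% is √(0.16 × 0.84/4000) = 0.6 points. Stopping rates are combination/control.
- Rule A: last contact (Section 10.5).
- Rule B: living stoppers censored at last scan, deaths still counted.
- Rule C: every stopper censored at last scan, later deaths not counted.

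| Stopping | Measure | A | B | C |
|---|---|---|---|---|
| 0/0 | Type I error | 11% | 11% | 11% |
| 20/10 | Type I error | 16.2% | 13.4% | 11.0% |
| 30/10 | Type I error | 22.7% | 16.5% | 10.6% |
| 10/10 | Power | 86.8% | 89.1% | 89.8% |
| 10/20 | Power | 77.0% | 85.7% | 88.8% |

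Repeat runs of 2,500 to 3,000 trials agree: 16-17% (A) and 13-14% (B) at 20/10; 21-25% (A) and 16-17% (B) at 30/10; 78% (A) and 86% (B) power at 10/20. At 10/10 the power loss under A is 89.1 − 86.8 = 2.3 points against B, 89.8 − 86.8 = 3.0 against C, and roughly 4 against the no-stopping benchmark.

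B recovers only part of the loss because, under the null, about two-thirds of stoppers die before the analysis and remain events at the date of death.

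**A different stopping pattern.** Here 20% stop at random after scan 0, 1 or 2, with a median of 6 to 12 months from progression to death.
- Combination arm only: type I error 23-30% (A) and 17-18% (B).
- Ipilimumab arm only: power 63-77% (A) and 84-86% (B).
- Both arms: type I error 11-12% under either rule; power 78-85% (A) and 84-87% (B). Nine-month PFS under the null is 20-22% (A) and 18% (B), against 15% when everyone is scanned.
- Not counting deaths after two missed assessments gives type I error of about 9-13% and power of 88-92% in these scenarios.

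**The case against.** The strongest reply is that the plan leaves little room for the problem. Scans are scheduled until progression in both arms, including after treatment ends. Section 8.3e says assessments continue when dosing is delayed, and Section 14.4 requires tumor forms until progression. Progression can also be recorded without a scheduled scan: Section 10.2 accepts new lesions and the physician's judgment of unequivocal progression, and symptomatic deterioration is itself a PFS event. The simulations give stoppers none of these events before death, so they sit at the upper end. All of that stands, and with no stopping the rule does no harm. But a requirement to scan is not a rule for patients who are not scanned, and the plan has none.

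Two stronger readings are tempting, and the documents support neither.

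- *That the rule favors the more toxic combination.* No stopping rate is given for either arm. Ipilimumab patients finish treatment after four cycles and might stop scanning more often. At 10/20 stopping, type I error under last contact falls to about 8%, and the damage is lost power.
- *That Arm 2 is contacted every 4 weeks and Arm 1 only every 12.* While adverse events persist, follow-up checks in Arm 1 are "Every 3 weeks until resolution of adverse events" and in Arm 2 "Every 4 weeks until resolution of adverse events". Arm 2's 28-day treatment visits apply to patients whose scans continue, so that contrast credits at most one scan interval.

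Censoring at the last assessment can also be informative if patients stop because they are about to progress. In simulations with that feature it still did better than last contact when stopping was unequal.

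**Conclusion.** The point holds. Section 10.5 credits unassessed time as progression-free in the primary analysis, and no other section corrects it. Direction depends on which arm loses more scans: equal stopping mainly overstates PFS in both arms and costs power, while unequal stopping can inflate the false-positive rate or cut power further.

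The figures rest on assumed stopping rates of 10 to 30% and an assumed 9-month median from progression to death. They show sensitivity and are not a forecast. A reader might also infer that moving the censoring date is enough; it is not, because later deaths remain events at the date of death. The change should be made, and it needs both parts.

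**What to change.** Replace the censoring sentence in Section 10.5 with:

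*Patients without a PFS event are censored at the date of the last adequate disease assessment (registration if none). A progression or death first recorded after two or more consecutive missed assessments is censored at the last adequate assessment before the gap.*

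Keep last-contact censoring with all deaths counted as a sensitivity analysis, and report by arm how many patients stopped assessment before a PFS event.

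Rule C in the table is slightly stricter than this wording, which still counts a death before a second assessment is missed; the 9-13% and 88-92% ranges apply the two-missed rule itself.

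The cost is a few sentences and one derivation from assessment dates already collected under Section 14.4. The downside is slightly less follow-up and a few fewer events in the primary analysis.

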10.6 Time to death

Measured from the date of registration until death from any cause, with patients last known to be alive censored at the date of last contact

11.0 STATISTICAL CONSIDERATIONS

11.1 Accrual Goal

Although the primary objective aims to assess whether combination therapy ipilimumab and nivolumab is superior to single therapy ipilimumab in patients who have previously progressed on anti-PD-1 or anti-PD-L1 therapy, major additional objectives of this study include assessment of key biomarkers and genomic correlatives, particularly for patients who receive combination therapy. This study will use a design in which 63 patients will be randomized to receive combination therapy ipilimumab and nivolumab and 21 patients will be randomized to receive single therapy ipilimumab. Assuming an ineligibility rate of 10% the total accrual goal is 94 patients.

The unbalanced randomization is motivated by the necessity of evaluating the first secondary objective. In particular, the underlying rationale for the combination therapy is that initial progression on PD-1 blockade alone results from poor T cell recruitment. If the combination therapy is superior to single agent ipilimumab, evaluation of this hypothesis by comparing T cell infiltration between patients who have an objective response (confirmed and unconfirmed partial or complete response per RECIST 1.1) and patients who do not have an objective response to combination therapy will elucidate mechanisms that are imperative for design and development of further studies of combination therapy in this population. Thus, unbalanced randomization is necessary to ensure adequate sample size for evaluating this hypothesis. Assuming a response rate of 25% and 90% compliance in tissue and biopsy submission, then we anticipate accruing 14 eligible objective responders and 43 eligible objective non-responders in the combination therapy arm.

11.2 Primary Analysis and Interim Analysis

For our primary objective, we will compare the PFS between arms using a log-rank test. Kaplan-Meier plots will be constructed and median PFS for each arm with corresponding 95% Brookmeyer-Crowley confidence intervals will be estimated.

Combination therapy will be considered superior to single therapy ipilimumab if median progression-free survival (PFS) is doubled. Based on Hodi et al., we assume the median PFS for patients randomized to single therapy ipilimumab to be 3 months such that the target alternative PFS for patients randomized to combination therapy is 6 months (corresponding to a hazard ratio of 0.5). We assume exponential survival, 24 months of accrual, 12 additional months of follow-up after the last patient is randomized, and that the final analysis will be conducted at the one-sided $\alpha = 10\%$ level. One interim analysis for futility will be performed after approximately 50% information under the null (corresponding to approximately 41 events across both arms which is expected to occur 16-17 months after accrual starts). If the hazard ratio favors the control arm (is greater than 1), the study will be stopped due to futility. Given the modest sample size, no plans for formal interim analysis of efficacy are included. Using simulations (10,000 replicates), this design has overall type I error of 9.0% and power of 89%. Under the null, the probability of stopping early for futility at the interim analysis is 50% and under the alternative, the probability of stopping early is 4.1%.

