
For non-clinical questions (i.e. unrelated to patient eligibility, treatment, or clinical data submission) contact the CTSU Help Desk by phone or e-mail: CTSU General Information Line – [name], or [contact]. All calls and correspondence will be triaged to the appropriate CTSU representative.
		

The CTSU Website is located at https://www.ctsu.org.
		

SCHEMA

Locally advanced or metastatic melanoma that has progressed on anti-PD-1 or anti-PD-L1 treatment

NOTE: This study includes mandatory specimen submission. See [Section 15.0](#) for details.

* For every patient randomized to receive standard of care, there will be three randomized to receive the experimental regimen (see [Section 11.0](#)).

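### The standard log-rank test at 63:21 has type I error of about 11%, not the 9.0% stated in Section 11.2; the four simulated operating characteristics need restating with their settings

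*Combined protocol and SAP*

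**What the plan says.** Section 11.1 fixes the allocation: "63 patients will be randomized to receive combination therapy ipilimumab and nivolumab and 21 patients will be randomized to receive single therapy ipilimumab". The Schema note agrees: "For every patient randomized to receive standard of care, there will be three randomized to receive the experimental regimen".

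Section 11.2 names the test: "For our primary objective, we will compare the PFS between arms using a log-rank test". The level is one-sided 10%, and the medians are 3 months (ipilimumab) and 6 months (combination), a hazard ratio of 0.5. On timing it says: "We assume exponential survival, 24 months of accrual, 12 additional months of follow-up after the last patient is randomized".

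The futility look is described as follows: "One interim analysis for futility will be performed after approximately 50% information under the null", which it equates to "approximately 41 events across both arms which is expected to occur 16-17 months after accrual starts". The study stops if the hazard ratio is above 1, and there is no efficacy look.

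The reported results are "Using simulations (10,000 replicates), this design has overall type I error of 9.0% and power of 89" percent, a 50% chance of stopping early under the null, and "under the alternative, the probability of stopping early is 4.1" percent. No variance form, alternative cutoff, accrual pattern or loss rate is given, and nothing says whether the futility stop is binding.

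**The concern.** Section 11.2 is the only place that states the error risks of the primary comparison and of the futility rule. A type I error of 9.0% looks plausible, because a futility stop lowers a nominal 10% somewhat. But with 3:1 allocation and about 80 events the log-rank statistic is skewed, and its error in favour of the larger arm exceeds nominal. If the stated figure does not belong to the test that will be run, readers will think the primary result is protected at 9% when the actual risk is about 11%. The other stated figures also differ from what the inputs give.

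**Working it through.** **Inputs.** From 11.1: 63 + 21 = 84 eligible patients. From 11.2: the medians, exponential PFS, 24 + 12 months, one-sided 10% (Z > 1.2816), and a stop at 41 events if HR > 1. My assumptions where the text is silent: uniform accrual, no loss, futility obeyed.

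**1. The plan's event count and timing reproduce.** The hazards are ln2/3 = 0.2310 (null, and control) and ln2/6 = 0.1155 (combination under the alternative).

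- Expected events at month 36 are n × [1 − (e^(−12λ) − e^(−36λ))/(24λ)]. Under the null: 84 × [1 − (0.0625 − 0.0002)/5.545] = 83.1. Half is 41.5, so about 41 events is right.
- Expected events at month t ≤ 24 are (n/24) × [t − (1 − e^(−λt))/λ]. Under the null at month 16: 3.5 × (16 − 4.22) = 41.2, so the 16-month projection is right.
- Under the alternative at month 16: 0.875 × 11.78 + 2.625 × 8.71 = 33.2 events. The 41st event comes on average at 18.3 months.
- Under the alternative at month 36: 21 × 0.9888 + 63 × 0.9155 = 78.4 events.

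**2. Large-sample approximation.** The interim statistic has mean ln2 × √(41 × 3/16) = 0.693 × 2.773 = 1.92 under the alternative, so P(stop) = Φ(−1.92) = 2.7%, against 4.1% stated. The joint normal calculation gives type I error of 9.5% with 41 of 82 events, and power of 90.6% (78.4 final events) to 91.4% (82). This misses the stated power and false-stop figures too.

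**3. Simulation** (60,000 to 200,000 trials per hypothesis; ranges are across repeated runs).

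| Final statistic and interim look, 63:21 | Type I | Power | Stop, null | Stop, alternative |
|---|---|---|---|---|
| Section 11.2 | 9.0% | 89% | 50% | 4.1% |
| Standard log-rank, 41 events | 11.1–11.3% | 91.8–91.9% | 48.8–49.0% | 2.2–2.4% |
| Standard log-rank, fixed look at 16 months | 11.1–11.4% | 90.8–90.9% | 48.9% | 3.5–3.6% |
| Standard log-rank, fixed look at 17 months | 11.3% | 91.4–91.5% | 48.7–48.8% | 3.0% |
| Standard log-rank, 16 months, 20% annual loss | 11.2% | 88.9% | 48.8% | 4.1% |
| Design-variance score, 41 events | 8.9–9.0% | 89.8–90.0% | about 49% | 2.2–2.4% |
| Design-variance score, 16 months | 8.8–9.1% | 88.9–89.1% | about 49% | 3.5–3.6% |
| Design-variance score, 17 months, 6-month accrual ramp-up | 8.8–9.0% | 88.4–88.8% | about 49% | 4.0–4.3% |
| Permutation log-rank, 41 events | 9.7% | 90.6% | about 49% | about 2.3% |

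The standard log-rank uses the hypergeometric variance. The design-variance score is Z = (E − O)/√(d × 3/16), with O and E the observed and expected events in the combination arm and d the total events.

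**4. Why the standard test exceeds nominal.** Without the futility rule it rejects in 11.6–11.8% of null trials in favour of the larger arm and in about 9.1–9.2% in the other direction. Futility stopping removes only about 0.5 points. Across fixed looks, loss, ramp-up and progression seen only at 12-weekly scans, the standard test stayed at 10.3–11.4%.

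**5. Not simulation noise.** For 10,000 replicates the standard errors are √(0.112 × 0.888/10,000) = 0.32 points for type I error, √(0.919 × 0.081/10,000) = 0.27 for power, and √(0.0226 × 0.9774/10,000) = 0.15 for the alternative stop. Allowing for rounding of the stated values, the 41-event gaps are (11.2 − 9.05)/0.32 ≈ 7, (91.9 − 89.5)/0.27 ≈ 9 and (4.05 − 2.26)/0.15 ≈ 12 standard errors.

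**The case against.** The best defence is that the stated figures may be a correct result for settings the plan did not write down. This largely stands. A score standardised by d × 3/16, the variance behind the usual sample-size formula, gives about 9.0% and 89–90% at the stated allocation with the ordinary cutoff. Adding a ramp-up and a 17-month look brings the alternative stop to about 4.1%. So 9.0% is not out of reach at 63:21. But those choices are not in the documents, and an unqualified log-rank test is ordinarily the hypergeometric-variance version.

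A reader might infer that the simulation had the arms reversed, because 21 combination : 63 control gives 8.5%, 88.4%, 51.2% and 4.3%. The documents do not support this. Section 11.1 and the Schema agree on 3:1 in favour of the combination, the simulation code is not shown, and the design-variance score comes about as close at the stated allocation.

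A reader might also see two competing interim triggers. Section 11.2 reads more naturally as an event-count trigger, with the months as a projection. The projection holds under the null but is about two months early under the alternative.

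Finally, the consequence is modest. On the stated inputs without loss, the plan's power and false-stop figures err on the cautious side. Only the type I error errs the other way.

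**Conclusion.** The point holds in limited form. With the stated inputs and the standard log-rank, Section 11.2 should read about 11.2%, 92%, 49% and 2.3%, or about 11.3%, 91%, 49% and 3.0–3.6% for a fixed look at 16–17 months. Type I error is about 2.2 points above the stated figure and 1.2 above nominal; it is about 11.7% if the futility stop is overridden. This rests on uniform accrual, no loss and an obeyed stop. Relaxing accrual, loss or scan timing moves power and the alternative stop but leaves the standard test above 10%.

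It would be wrong to conclude that the trial is underpowered: power is at or above 89% on the stated no-loss inputs. Nor is the 9.0% shown to be a calculation error. It does not belong to the test as named, and the settings that might explain it are missing.

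**What to change.** 1. Re-run the simulation at 63:21 with the log-rank statistic that will be used at the final analysis, and restate all four figures in Section 11.2.
2. Beside them, state the test variance or cutoff, the interim trigger as an event count (with the months marked as a projection under the null), the accrual pattern, the loss assumption, and whether the futility stop is binding.
3. If 9.0% came from a design-variance or permutation test, specify that same test for the final analysis, so that the stated error rate applies to the reported result.
4. Optional, if 10% is meant as a ceiling: a simulation-calibrated cutoff of about Z ≥ 1.36 gives 10.0% with futility obeyed, and power falls from 91.9% to 90.8%, about 1 point.

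Fix the choice before the PFS comparison is seen. The cost is one simulation run and a few lines of text. Sample size and the stopping rule do not change.
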